8.7.3.2 Ferritin, Iron, TIBC, Vitamin D, Vitamin B12, Folate

Blood samples for Ferritin, Iron, TIBC, Vitamin D, Vitamin B12, and Folate are collected at Visits 3, 9, and 15.

The results from these tests will be provided in data listings.

8.7.3.3 Serum IgA

The results of the Serum IqA test at Screening will be provided in a data listing.

8.7.3.4 GGT

GGT is tested in the event ALP is >3 x ULN. The results of any applicable GGT testing will be presented in a data listing.

8.7.3.5 HbA1c

Subjects who have a history of Type 1 or Type 2 diabetes or subjects who present with glucose detection in urine should have HbA1c tested on study. The HbA1c results will be presented in a data listing.

8.7.4 Other Safety Variables

8.7.4.1 Vital Signs

Vital signs include BP, respiratory rate, heart rate, and body temperature (axillary or oral). Measurements of BP and heart rate will be assessed supine or sitting, after the subject has rested for at least 5 minutes in a quiet setting without distractions.

Descriptive statistics will be provided by visit and treatment group for all vital sign parameters. All vital signs will be further provided in a data listing.

A separate data listing will be provided showing all vital signs for subjects where a vital sign has met PCI criteria.

Cut-off values considered to be potentially clinically important (PCI) for vital signs are outlined in Appendix 11.3.

8.7.4.2 Weight

Descriptive statistics will be provided by visit and treatment group for body weight (kg). Means of both the absolute values and changes from baseline in weight will be presented graphically by visit and treatment group. Cut-off values considered to be potentially clinically important (PCI) for weight is outlined in Appendix 11.3.

8.7.4.3 Physical Examination

Physical examination results will be listed by treatment group, visit, body system, result (normal, abnormal, not done) and clinical significance (yes, no).

A separate data listing will be provided showing all physical examination results for subjects who experienced at least one abnormal and clinically significant result.

8.8 Pharmacokinetics and Immunogenicity

Blood samples for PK and anti-drug antibodies (ADA) will be collected before study drug administration (baseline) and at each visit before dosing (trough).

8.8.1 Pharmacokinetics

All analyses will be conducted using SAS version 9.4 or higher. All derivations, statistical analyses, summaries and listings will be generated using SAS version 9.4 or higher (SAS Institute, Inc., Cary, North Carolina). Graphics may be prepared using the same versions of SAS, or Phoenix® WinNonlin® 8.3 or higher (Certara, L.P. Princeton, New Jersey, United States of America [USA]).

Some minor modifications may be necessary to the planned design of tables, figures, and listings to accommodate data collected during the actual study conduct.

8.8.1.1 Serum Concentration Data

All PK concentrations will be reported and analyzed with the same precision as the source data provided by the bio-analytical laboratory regardless of how many significant figures or decimals the data carry.

A listing of PK blood sample collection times will be provided. Serum concentrations will be summarized using descriptive statistics by time point for PRV-015 treatment groups. Concentrations that are below the limit of quantitation (BLQ) will be treated as zero for the computation of descriptive statistics. Descriptive statistics for concentration time data will include n, mean, standard deviation (SD), median, Lower Quartile, Upper Quartile, minimum, maximum, Geometric mean and Geometric Coefficient of Variation (GCV). For the reporting of descriptive statistics, the mean, standard deviation and Geometric mean will be presented to one digit more precision than the source data. The minimum, median, maximum, Lower Quartile and Upper Quartile will be presented to the same precision as the source data. Geometric Coefficient of Variation will always be reported to 1 decimal place. A minimum of n=3 is required for all descriptive statistics to be generated. If n is less than 3, only N, n, minimum, and maximum will be reported.

A subject listing of all concentration time data for each treatment will be presented. Figure of arithmetic mean concentration-time data (\pm SD, as appropriate) will be presented for PRV-015 treatment on linear and semi-logarithmic scales. Individual subject concentration-time data will be graphically presented on linear and semi-logarithmic scales.

No imputations will be done for missing data. Individual concentrations will be reported to the same precision as the source data.

8.8.1.2 Pharmacokinetic Analysis

Pharmacokinetic analysis will be done on PK analysis set.

PRV-015 trough concentrations (C_{min}) is the trough concentration which will be the pre-dose concentration for respective visits. PRV-015 trough concentrations (C_{min}) will be summarized using descriptive statistics by time point for PRV-015 treatment groups. Concentrations that are below the limit of quantitation (BLQ) will be treated as zero for the computation of descriptive statistics. Descriptive statistics for concentration time data will include n, mean, standard deviation (SD), median, Lower Quartile, Upper Quartile, minimum, maximum, Geometric mean and Geometric Coefficient of Variation (GCV). For the reporting of descriptive statistics, the mean, standard deviation and Geometric mean will be presented to one digit more precision than the source data. The minimum, median, maximum, Lower Quartile and Upper Quartile will be presented to the same precision as the source data. Geometric Coefficient of Variation will always be reported to 1 decimal place. A minimum of n=3 is required for all descriptive statistics to be generated. If n is less than 3, only N, n, minimum, and maximum will be reported.

In addition, dose proportionality, achievement of steady-state, and accumulation ratio based on Cmin will be assessed.

Dose Proportionality:

Dose proportionality of C_{min} will be assessed separately for PK sampling Day 15 (Visit 4) and Day 169 (Visit 15) using the power model (C_{min} = a * Dose^{β}), along with an "estimation" interpretation, according to the recommendations in Gough et al. (1995). The power model will be fitted on the log-transformed scale as:

 $log(Y_i)=a + \beta*log(Dose_i)+\epsilon_i$

where Y_i and Dose; are the C_{min} value and dose value for subject i, respectively, ϵ_i is the random error, α is the intercept parameter and β is the slope parameter. The power model parameters will be estimated using least -squares (LS) regression and presented with 90% CIs. Model lack-of-fit will be assessed by residual plots, and by an F-test of the residual mean square versus the pure error residual mean square. If the model fit is adequate, point estimate and 90% CI for β will be obtained, and used to obtain point estimates and 90% CIs for the increase in C_{min} associated with an r-fold (r=2 and r=high dose / low dose) increase in dose, by exponentiating r to the power of the β point estimate and confidence limits, $r^{\beta \pm t \times SE(\beta)}$. If there is evidence of model lack-of-fit, then an ANOVA model on the log-transformed C_{min} with dose as fixed categorical effect will be used. Point estimate and 90% CI, associated with mean difference between pairwise dose increases, obtained from this model will be converted back to the original scale using the antilog transformation.

Accumulation ratio:

For C_{min} , individual accumulation ratio Rac C_{min} at Day 169 will be calculated as C_{min} at Day 169/ C_{min} at Day 15. A listings of individual accumulation ratios will be provided, along with their descriptive statistics (arithmetic mean, standard deviation, geometric mean, coefficient of variation (%), median, minimum and maximum).

Accumulation versus Day 15 (Visit 4) will be assessed for Day 169 (Visit 15) using an ANOVA model on the log-transformed accumulation ratio (Rac C_{min}) with dose as fixed categorical effect. Point estimates and 90% CI obtained, by dose level and overall, from this model will be converted back to the original scale using the antilog transformation.

Achievement of steady-state:

Steady state on Cmin (ie, Ctrough) will be assessed using a nonlinear mixed model (Hoffman et al, 2005):

$$C_{ij} = C_{ss}e^{c_i}(1 - e^{-(\gamma e^{g_i}j)})e^{\varepsilon_{ij}}$$

where C_{ij} is the observed trough (C_{min}) plasma concentration for the ith subject on Day j, C_{SS} is the average steady state trough (C_{min}) plasma concentration, γ is the average first-order elimination rate, $\epsilon_{ij} \sim N(0, \sigma^2_e)$ is the random within-subject error, and c_i and g_i are the random individual deviations from C_{SS} and γ , respectively, such that

 $(c_i, g_i) \sim N([0, 0], \Sigma)$ with

$$\Sigma = \begin{bmatrix} \sigma_c^2 & \sigma_{cg} \\ \sigma_{cg} & \sigma_g^2 \end{bmatrix}$$

The model assumes a log-normal distribution for both the within-subject erros (ϵ_{ij}) and the random effects c_i and g_i . The above nonlinear model analysis will be based on the log-transformed C_{min} values. Data from all subjects together from all dose groups will be used for the analysis.

Time (t_{ss} in days) at which 90% of the subject-specific C_{ss} is achieved (ie, individual steady state attainment) will be calculated from the model, using the equation:

$$t_{ss} = \frac{\log(1 - 0.9)}{-\gamma}$$

Similarly, time (in days) at which 50% of the subject-specific C_{ss} is achieved (ie, average steady state attainment) will also be provided.

In addition, model parameter estimates with standard errors and 90% CIs will be provided. The adequacy of the nonlinear model will be assessed graphically by plotting residual versus dose, residual versus time, and observed (log-scale) and predicted values versus time for individual subjects.

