Abbreviations: ADA=anti-drug antibody; BP=blood pressure; BSFS=Bristol Stool Form Scale; CeD PRO=Celiac Disease Patient Reported Outcome; DGP=deamidated gliadin peptide; ECG=electrocardiogram; EGD=esophagogastroduodenoscopy; Early Term=early termination; FSH=follicle-stimulating hormone; GSRS=Gastrointestinal Symptom Rating Scale; HbA1C=hemoglobin A1C; HBV=hepatitis B virus; HCV=hepatitis C virus; HIV=human immunodeficiency virus; HLA=human leukocyte antigen; IGA=Investigator Global Assessment; LH=luteinizing hormone; PGIC=Patient Global Impression of Change; PGIS=Patient Global Impression of Severity; PK=pharmacokinetics; QoL=quality of life; TIBC=total iron binding capacity; tTG=tissue transglutaminase; WOCBP=women of childbearing potential, non-WOCBP=women not of childbearing potential.

1. Testing for COVID-19 infection (including viral RNA testing for acute infection and/or antibody testing for past exposure) may be conducted if appropriate.
2. Visits 6, 8, 10, and 12 may be conducted remotely by certified mobile healthcare personnel per Investigator's decision.
3. A complete physical examination is required at screening, Visit 1, Visit 15, and Visit 16. At other visits, the physical examinations are symptom directed.
4. Vital signs (including temperature, BP, heart rate, and respiratory rate) will be measured prior to each study drug administration. Vital signs will be taken again 30 minutes after study drug administration.
5. Blood and urine samples will be collected for hematology, chemistry, and urinalysis. In addition, HbA1c should be measured in those subjects with diagnosis of Type 1 or Type 2 diabetes only. If glucose is detected in the urine, HbA1c should be tested and the subject should receive clinical evaluation for diabetes per standard of care.
6. The screening blood samples include HIV, HBV, HCV, and IGRA tests. In addition, a test for HLA DQ2 and/or DQ8 typing will be performed if a previous report is not supplied.
7. Stool gluten samples will be collected by the subject the day before each scheduled visit or during the visit (with a window of 3 days before or after the visit). Urine gluten samples will be collected at the time of the office visit.
8. Blood samples for PK and ADA analyses should be collected before study drug administration (baseline) and at each visit before dosing (trough). The exact time and date of sample collection must be recorded. ADA analysis includes neutralizing antibodies (NAb).

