7.1. Discontinuation of Study Treatment

In rare instances, it may be necessary for a subject to permanently discontinue (definitive discontinuation) study treatment. If a subject discontinues study drug administration after randomization (Visit 3), the subject will be encouraged to return for all subsequent on-site visits as listed in the SoA (i.e., Visits 4, 5, 7, 9, 11, 13, 14, 15, and 16). If the discontinued subject chooses to not return for on-site visits, study personnel should make every effort to conduct the Early Termination (ET) visit and ask the subject to return 6 weeks after the last dose of the study drug for the final safety follow-up visit (see Section 1.3). If a subject discontinues study drug administration before randomization, no further assessments will be conducted.

The reasons for permanent discontinuation of study treatment at any time during the study include but are not limited to the following:

- Safety reasons, either at the discretion of the Investigator or at the subject's request.
 - In particular, subjects can be discontinued from study treatment if they develop severe complications of celiac disease that require intensive treatment (e.g., RCD-I or RCD-II, jejunitis, perforation).
 - Malignancy
 - Active TB
 - A serious opportunistic infection
 - Pregnancy (female subjects)
 - Anaphylaxis or severe hypersensitivity reactions after the initial injection(s)
- Significant protocol violations (e.g., noncompliance with study procedures), at the discretion of the Sponsor
- The use of prohibited therapy that may interfere with the study assessment and analysis (Section 6.5.1). The Investigator is required to report all such information on the CRF and decide, upon discussion with the Sponsor, whether the subject is to be discontinued from study treatment.

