8.1.6 Pharmacokinetics (PK) analysis set

The PK analysis set includes subjects who are randomized, dosed, and have at least 1 postdose evaluable PK assessment.

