8.2.4 Handling of Data from Discontinued Subjects

Generally, the data from subjects who discontinue the study will be presented up to the point of discontinuation. Subjects who discontinue the study prior to randomization will not be included in ITT, mITT, PP or safety analysis set. Subjects who permanently discontinue the treatment will be included in the analysis set(s) based on the analysis set inclusion definition.

A subject who permanently discontinues treatment will be encouraged to return for all subsequent on-site visits as listed in the SoA (Appendix 11.1), i.e., Visits 4, 5, 7, 9, 11, 13, 14, 15, and 16. If the discontinued subject chooses to not return for on-site visits, the Early Termination (ET) visit should be done and subject is asked to return 6 weeks after the last dose of the study drug for the final safety follow-up visit.

If subject decides to permanently discontinue the study, the early termination assessments listed for Visit 15 (Week 24) should be conducted before the withdrawal, including EGD and biopsy, unless the withdrawal occurs before randomization.

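### Cmin is defined by visit with no time-since-dose rule, so washout samples from subjects off drug can enter the Day 169 trough, accumulation and dose-proportionality results

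*SAP*

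**What the plan says.** SAP 8.8.1.2 says that Cmin "is the trough concentration which will be the pre-dose concentration for respective visits". Two model-based analyses then use Day 169:

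- Dose proportionality of Cmin "will be assessed separately for PK sampling Day 15 (Visit 4) and Day 169 (Visit 15) using the power model".
- "Accumulation versus Day 15 (Visit 4) will be assessed for Day 169 (Visit 15) using an ANOVA model on the log-transformed accumulation ratio". The ratio is each subject's Day 169 Cmin divided by the Day 15 Cmin.

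The steady-state model in the same section pools data from all subjects and dose groups.

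On who contributes, SAP 8.1.6 says: "The PK analysis set includes subjects who are randomized, dosed, and have at least 1 postdose evaluable PK assessment". SAP 8.2.4 adds: "Subjects who permanently discontinue the treatment will be included in the analysis set(s) based on the analysis set inclusion definition". Under Protocol 7.1, after stopping study drug "the subject will be encouraged to return for all subsequent on-site visits as listed in the SoA", and Visit 15 is among the visits named. The schedule of activities takes a PK sample at Visit 15, while dosing ends at Visit 14 (Day 155). On timing, footnote 8 of the protocol schedule says: "The exact time and date of sample collection must be recorded". SAP 8.8.1.1 lists sample collection times but does not use them to decide what counts as a trough.

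**The concern.** A trough is the level at the end of a dosing interval, here 14 days after a dose. A subject who stopped weeks earlier and attends Visit 15 gives a washout level. A subject who missed only the Visit 14 dose gives a 28-day level. Nothing in the SAP separates either from a true 14-day trough.

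The power model and the accumulation ANOVA work on the log scale, where a few very low values carry much weight. Cmin is the named secondary PK endpoint. Accumulation that is understated, or a proportionality estimate made imprecise or shifted, would describe a mixture of on-drug and off-drug subjects rather than the regimen.

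**Working it through.** The plan states no figure for these analyses, so there is nothing to reproduce. The check is of the rules first, then of the possible size.

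**Rules.**
1. Visit 15 falls 169 − 155 = 14 days after the last planned dose. For a fully dosed subject the Day 169 sample is therefore a sound trough, though no dose follows it.
2. A strict pre-dose reading would remove every Day 169 value the SAP plans to use. A loose reading admits every Visit 15 sample. Neither separates on-drug from off-drug subjects.
3. The PK set is a subject-level entry rule that one sample satisfies. Its word evaluable is not defined and is not applied sample by sample. The 80% compliance criterion in SAP 8.1.5 belongs to the per-protocol set.
4. The steady-state equation contains 1 − exp(−γ·exp(gᵢ)·j), which only increases with study day j. It cannot describe falling levels.

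**Size (assumptions, not document figures).** Assume mono-exponential decline, a half-life T of 14, 21 or 28 days, a last dose on Day 85, and washout values that stay quantifiable. The Day 169 sample is then 84 days after the last dose, 70 days later than a trough should be.

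- Level relative to the on-treatment trough: r = 2^(−70/T), treating the on-treatment trough as already at its plateau.
- With a share f of off-drug attenders, the geometric mean Day 169 Cmin is multiplied by r^f. So is the geometric mean accumulation ratio, because its Day 15 denominator is unaffected.
- Slope shift with shares p at 100/300/600 mg and equal n: regress p·ln(r) on ln(dose). Centred ln(dose) is −0.963, 0.135, 0.828, with sum of squares 1.633. For p = 5/10/15%, the slope of p on ln(dose) is (−0.963×0.05 + 0.135×0.10 + 0.828×0.15)/1.633 ≈ 0.055. This is multiplied by ln(r) = −3.466, −2.310 or −1.733. For p = 1/2/3% it is one fifth of that.

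| T (days) | r | Fall, f = 2% | Fall, f = 10% | Slope shift, 5/10/15% | Slope shift, 1/2/3% |
|---|---|---|---|---|---|
| 14 | 0.031 | 6.7% | 29% | −0.19 | −0.04 |
| 21 | 0.099 | 4.5% | 21% | −0.13 | −0.03 |
| 28 | 0.177 | 3.4% | 16% | −0.10 | −0.02 |

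**Cross-check by full superposition of 12 two-weekly doses.** For subjects who stop after six doses (last dose Day 71), the Day 169 level is 1.5%, 5.9% and 11% of the full-course trough at the same half-lives. With 9.1% of an arm stopped, a share borrowed for illustration from (55 − 50)/55, the geometric mean accumulation ratio falls from 2.00 to 1.37, 2.69 to 2.08 and 3.36 to 2.75 (−32%, −23%, −18%). Missing only the Visit 14 dose leaves 50%, 63% and 70% of the full-course trough.

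**Equal stopping across doses.** A simulation with 50 per dose, a true slope of 1, an assumed between-subject CV of 40% and 9.1% stopped after six doses in every arm gave a mean slope of about 1.00. The 90% interval width grew from 0.14 to 0.46, 0.33 and 0.27. This is lost precision, not bias.

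**The case against.** A reader might infer that the SAP treats every scheduled-visit concentration as a trough. The text does not go that far. At Visits 4 to 14, a sample from someone who has stopped drug precedes no dose, so the pre-dose wording can be read to exclude it. That objection stands for those visits. It does not help at Visit 15, and it does not deal with a sample taken after a missed dose when dosing then resumes.

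A reader might also infer that a truly proportional drug would be shown as sub-proportional, or that dose selection would be misled. Neither is supported. The slope moves only if stopping differs by dose, and the documents give no such pattern. The separate Day 15 power model follows the first dose and is untouched by later stopping, so a discrepancy between the two days would be visible. Protocol 9.2 rests the choice of dose on the totality of evidence, not on these PK models.

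Protocol 7.1 describes permanent discontinuation as rare and lets a subject choose the early-termination visit instead of continued attendance. The 10% share may therefore be too high, and the 2% column is the fairer low case. The planned allowance of about 50 evaluable among 55 randomized is not defined as off-drug attendance.

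The SAP also plans diagnostics: individual concentration plots, sample-time and injection listings, individual ratios, residual plots and a lack-of-fit test. These would make washout values visible, but they do not remove them.

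Finally, some washout values may be below quantitation. SAP 8.2.3 assigns half the limit, SAP 8.8.1.1 and 8.8.1.2 assign zero for descriptive statistics, and zero cannot be logged. The calculated falls hold only for quantifiable values.

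**Conclusion.** The point holds, centred on Day 169. Applied as written, the plan puts washout levels from subjects who have stopped drug, or missed the Visit 14 dose, into the Day 169 Cmin summary, the Day 169 power model and the accumulation ratio. It also puts them into a steady-state model that cannot represent them. The direction is certain for quantifiable values: geometric mean Cmin and accumulation are pulled down. For the slope, the expected effect is a wider interval, with bias only under dose-related stopping.

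The size is not known. About 3-7% (2% off-drug attenders) to 16-29% (10%) is an illustration that rests on the assumed half-life, stopping day and shares. The primary efficacy analysis is not involved. This is worth correcting before unblinding because a named secondary endpoint is affected and the correction is cheap.

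**What to change.** In SAP 8.8.1.2, define an evaluable trough by actual time since last dose. One workable rule: a sample taken 14 ± 4 days after a complete scheduled dose (all four injections) and before any next dose, with the scheduled dose before that one also received (not required at Visit 4). The ± 4 days follows from the ± 2-day windows on two consecutive visits.

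Use only these samples for the Cmin summaries, the Day 169 power model, the accumulation ratio and the steady-state fit. List all other concentrations with time since last dose, and give an all-samples summary as supportive. State how values below quantitation enter the log-scale models, and reconcile SAP 8.2.3 with 8.8.1.1 and 8.8.1.2.

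The work is SAP wording and one derived flag. Sample times are recorded under the schedule's footnote 8, and dose dates and times under Protocol 6.4. There are three costs:

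- The n at Day 169 is slightly smaller.
- The estimates describe exposure while on drug and are conditioned on staying on treatment. If subjects with low exposure stop more often, Cmin and accumulation would be biased upward, which is why the all-samples summary should stay.
- A two-dose rule still admits someone who missed several earlier doses and recently resumed. The team may prefer a longer run of consecutive doses for the Day 169 analyses.
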